4.1.8 Definition of evaluable patient

For decisions on dose escalation, an evaluable patient is defined as a patient who has received BI 836880 or BI 836880 plus BI 754091 and either:

- has completed cycle 1 without experiencing DLT

OR

- has experienced DLT during cycle 1

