3.3.4.1 Discontinuation of trial treatment

An individual patient will discontinue trial treatment if:

- The patient wants to discontinue trial treatment, without the need to justify the decision.
- The patient has repeatedly shown to be non-compliant with important trial procedures and, in the opinion of both, the investigator and sponsor representative, is not willing or able to adhere to the trial requirements in the future.
- The patient needs to use concomitant medication that interferes with the investigational medicinal product or trial assessments. Refer to Section [4.2.2.1](#) for prohibited concomitant medications.
- The patient can no longer receive trial treatment for medical reasons (such as surgery, adverse events, other diseases, or pregnancy). Refer to Section [4.1.6](#) for AEs that require treatment discontinuation.
- The patient experiences unequivocal PD by RECIST v1.1 and/or iRECIST (iRECIST applies to Part II only). Refer to Section [5.1.1](#) for details.

Even if the trial treatment is discontinued, the patient remains in the trial and, will undergo the procedures for the end of treatment (EoT) visit and follow up as outlined in the [Flow Chart](#) and Section [6.2.3](#).

For all patients the reason for withdrawal from trial treatment (e.g. AEs) must be recorded in the CRF. These data will be included in the trial database and reported.

During the dose finding part, patients withdrawn for a reason other than having a DLT or patients who miss more than one visit during MTD evaluation period may be replaced after discussion in the SMC if the information that needed to be collected during that visit is not available and makes the patient non-evaluable for the PK analyses or safety parameters (including evaluation for DLTs).

Patients who come off trial due to a DLT will not be replaced.

If a patient should become pregnant during the trial, the study treatment must be immediately stopped. The patient will be followed up until delivery or termination of pregnancy (see Section [5.2.9.2.3](#) for information on pregnancy forms). The data of the patient will be collected and reported in the electronic case report form (eCRF) until the last patient's last visit and any events occurring thereafter will be reported in the BI drug safety database.

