If symptoms of an infusion-related reaction CTCAE grade ≤ 2 , but not qualifying as DLT according to Section [4.1.7](#) occur, the infusion should be temporarily stopped. Upon recovery, it should be infused at 50% of the rate at which the reaction occurred. Depending on the time of occurrence and the severity of the reaction, the investigator may consider administering additional supportive medication, e.g. corticosteroids for re-introduction. Infusion rate and premedication for further treatment cycles should be adapted according to Investigator decision.

In the combination treatment, BI 836880 and BI 754091 will be given as two separate consecutive intra-venous infusions. BI 754091 should be administered first, and BI 836880 will be administered approximately 15 minutes after the end of this infusion of BI 754091.

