If a patient experiences an infusion-related reaction, acetaminophen and/or an antihistamine (e.g., diphenhydramine) and/or corticosteroid or equivalent medication per institutional standard may be administered prior to subsequent infusions at the discretion of the Investigator for secondary prophylaxis of infusion-related reactions. If an infusion-related reaction is Grade 3 or higher in severity at any point during the study, treatment with BI 836880 and/or BI 754091 will be permanently discontinued.

As with any mAb, allergic reactions to study medication administration are possible. Appropriate drugs and medical equipment to treat acute anaphylactic reactions must be immediately available, and trial personnel must be trained to recognize and treat anaphylaxis. The trial site must have immediate access to emergency resuscitation teams and equipment in addition to the ability to admit patients to an intensive care unit if necessary.

The following terms describe those events that are to be considered potential infusion-related AEs. Regardless of grade, these events are considered as AESIs and must be reported to the sponsor within 24 hours of the event:

- Allergic reaction
- Anaphylaxis
- Cytokine-release syndrome
- Serum sickness
- Infusion reactions
- Infusion-like reactions

If the Investigator determines that another event (not on the list) may be a potential infusion related AE, the Investigator may also report that event as an AESI.

Hepatic injury

A potential hepatic injury is defined by the following alterations of hepatic laboratory parameters in patients with normal aminotransferase levels at baseline:

Proprietary confidential information © 2019 Boehringer Ingelheim International GmbH or one or more of its affiliated companies

- an elevation of AST (Aspartate Aminotransferase) and/or ALT (Alanine Aminotransferase) ≥ 3 fold ULN combined with an elevation of total bilirubin ≥ 2 fold ULN measured in the same blood draw sample, or
- aminotransferase (ALT, and/or AST) elevations ≥ 10 fold ULN.

A potential hepatic injury is defined by the following alterations of hepatic laboratory parameters in patients with abnormal aminotransferase levels of $>$ ULN and ≤ 2.5 fold ULN at baseline:

- an elevation of AST and/or ALT ≥ 3 fold the baseline value combined with an elevation of bilirubin ≥ 2 fold the baseline value measured in the same blood draw sample, or
- aminotransferase (ALT, and/or AST) elevations ≥ 10 fold the baseline value.

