7.3 PLANNED ANALYSES

No per protocol set will be used in the analysis. However, important protocol deviations will be summarised. The TSAP will specify the important protocol deviations in detail.

For the determination of the MTD, only MTD evaluable patients will be considered. For the analysis of secondary and further endpoints, all patients in the treated set (i.e. patients treated with at least one dose of trial medication) will be included in the analysis. Any other analysis sets will be defined in the TSAP.

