6.3 SUBJECT SETS ANALYSED

Treated set (TS) in monotherapy:

This patient set includes all patients enrolled in the trial who were documented to have administrated at least one dose of BI 836880 monotherapy. The TS is used for both efficacy analysis and safety analyses.

Treated set (TS) in combination therapy:

This patient set includes all patients enrolled in the trial who were documented to have administrated at least one dose of BI 836880 and ezabenlimab combination therapy. The TS is used for both efficacy analysis and safety analyses.

Dose escalation cohort treated set in monotherapy:

This patient set includes all patients enrolled in dose escalation cohort of monotherapy who were documented to have administrated at least one dose of study medication and were evaluable for the MTD determination. This set is used for dose finding and MTD determination in Part I.

Dose escalation cohort treated set in combination therapy:

This patient set includes all patients enrolled in dose escalation cohort of combination therapy who were documented to have administrated at least one dose of study medication and were evaluable for the MTD determination. This set is used for dose finding and MTD determination in Part II.

PK parameter analysis set (PKS)

The PK parameter analysis set (PKS) includes all subjects from the TS who provide at least one PK parameter that is not excluded.

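### Read literally, protocol 4.1.8 makes a Part II patient with a cycle 1 DLT on BI 754091 who never receives BI 836880 non-evaluable, contradicting the sections that count cycle 1 DLTs

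*Protocol*

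**What the plan says.** **Evaluability.** Protocol 4.1.8: "an evaluable patient is defined as a patient who has received BI 836880 or BI 836880 plus BI 754091 and either" has finished cycle 1 DLT-free or has had a DLT during cycle 1. Receipt of BI 836880 is common to both listed routes.

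**Infusion order in Part II.** Protocol 4.1.5: "BI 754091 should be administered first, and BI 836880 will be administered approximately 15 minutes after the end" of the first infusion.

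**Stopping rules.** Under protocol 4.1.6 a DLT stops trial drug administration at least temporarily, and the two drugs are handled together unless the event can be attributed to one of them. For an infusion-related reaction of Grade 3 or higher, protocol 5.2.9.1.4 says that "treatment with BI 836880 and/or BI 754091 will be permanently discontinued". Protocol 4.1.7 lists no exception for infusion reactions from its Grade 3 non-haematological DLT criterion.

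**MTD analysis.** Protocol 7.3: "For the determination of the MTD, only MTD evaluable patients will be considered". The Part II dose escalation set in SAP 6.3 also requires evaluability for MTD determination.

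**Treated set.** Protocol 7.3: for secondary and further endpoints, "all patients in the treated set (i.e. patients treated with at least one dose of trial medication) will be included". Protocol 7.3.1 repeats that definition and 7.3.5 puts all treated patients in the safety analysis. SAP 6.3 defines the Part II treated set by "at least one dose of BI 836880 and ezabenlimab combination therapy", and SAP 7.8 runs all safety analyses on the treated set. SAP section 4 declares no change to the planned analysis.

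**Replacement.** Protocol 3.3.4.1: "Patients who come off trial due to a DLT will not be replaced".

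**The concern.** The order of infusion creates a period in which a Part II patient has been exposed to BI 754091 only. If a DLT in that period means that BI 836880 is never given, the patient has a cycle 1 DLT on the combination regimen but fails the receipt condition in 4.1.8. The condition then removes the patient because of the toxicity that the trial is counting. Such an exclusion can only lower the observed DLT rate.

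The primary endpoint is the MTD and the number of patients with DLTs, from cohorts of about three. One DLT more or less can decide whether a dose meets EWOC. Two statisticians following different sections of the same documents could report different DLT counts for the same cohort.

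**Working it through.** **1. The passages side by side, for a Part II patient with a cycle 1 DLT on BI 754091 and no BI 836880**

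| Section | Effect on this patient |
|---|---|
| Protocol 4.1.8 | Not evaluable: BI 836880 not received |
| Protocol 7.3; SAP 6.3 dose escalation set | Out of the MTD analysis, because not evaluable |
| Protocol 4.1.7 | The DLT falls in the MTD evaluation period, so it counts |
| Protocol 7.3.2; SAP 7.4 | Only stops or non-completion for reasons other than a DLT are named as excluded |
| Protocol 7.3, 7.3.1, 7.3.5 | In the treated set and the safety analysis |
| SAP 6.3 combination treated set | Out if the phrase means both drugs received; in if it names the regimen |
| Protocol 3.3.4.1 | Not replaced if the patient comes off trial for the DLT |

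The first two rows conflict with the next two.

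**2. Reproducing the plan's own figures**

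Inputs: the Part II model in protocol 7.1.2 (reference doses 500 mg and 240 mg), the mixture priors of Table 7.1.2: 5 (weights 0.9 and 0.1), and the EWOC limit P(DLT rate ≥ 0.33) < 0.25. With BI 754091 fixed at 240 mg:

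- logit(π1) = log α1 + β1·log(d1/500); logit(π2) = log α2
- π0 = π1 + π2 − π1·π2; odds(π12) = odds(π0)·exp(η·d1/500)
- prior draws weighted by π12^r·(1 − π12)^(n − r) for r DLTs in n patients at each dose

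By Monte Carlo (6 million draws), the printed results reproduce only when the BI 836880 and BI 754091 rows of Table 7.1.2: 5 are exchanged:

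| Overdose probability | Printed | Recomputed, rows exchanged |
|---|---|---|
| Prior at 120, 360, 500, 720 | 0.187, 0.409, 0.653, 0.822 | 0.185, 0.404, 0.651, 0.823 |
| 120/240 after 0/3, 1/3, 2/3 there | 0.054, 0.228, 0.528 | 0.055, 0.225, 0.532 |
| 360/240 after 0/3 at 120/240 | 0.248 | 0.253 |
| 360/240 after 0/3 at 120/240, then 0/3, 1/3, 2/3 at 360/240 | 0.085, 0.295, 0.602 | 0.083, 0.294, 0.605 |

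With the rows as labelled, the prior at 120/240 is 0.422 against the printed 0.187. The exchanged rows are used below because they match the plan's tables.

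**3. Effect of dropping one DLT patient**

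| Data | DLT counted | DLT patient dropped |
|---|---|---|
| 0/3 at 120/240, then one DLT in three at 360/240 | 1/3: 0.294 at 360/240 (printed 0.295), fails EWOC | 0/2: 0.120 at 360/240, meets EWOC |
| One DLT in three at 120/240 | 1/3: 0.225 at 120/240 and 0.498 at 360/240; stay at 120/240 | 0/2: 0.291 at 360/240, still blocked |

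In the first case the printed scenario 5 de-escalates to 120/240. With the DLT dropped, 360/240 stays admissible and 500/240 does not (0.432). The change is therefore staying at 360/240 instead of de-escalating. Using the rows as labelled gives 0.380 and 0.186 at 360/240, the same switch across 0.25.

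**4. How often**

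Tables 7.1.2: 2 and 7.1.2: 3 show 0 DLTs in 3 + 34 + 3 + 6 = 46 BI 754091 monotherapy patients. One-sided 95% upper bound: 1 − 0.05^(1/46) = 0.063, for any DLT in the evaluation period. DLTs that arise before BI 836880 starts and prevent it are a subset. The documents give no rate for that subset. At assumed rates of 1%, 2% and 5% per patient, the chance of at least one in about 15 Part II patients is 1 − 0.99^15 = 14%, 1 − 0.98^15 = 26% and 1 − 0.95^15 = 54%.

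**The case against.** The strongest reply is that the documents show an intent to count these DLTs. Protocol 4.1.7 says that DLTs in the evaluation period are considered for the MTD, and protocol 7.3.2 and SAP 7.4 exclude only patients who stop for other reasons. The SMC reviews all patients and discusses evaluability (Table 1.4.2: 1), and DLTs are reported within 24 hours as AESIs. The event would be seen before a dose decision. This stands as evidence of intent. It does not settle the matter: those sections say who is excluded, not who is evaluable, and 4.1.8 is the only written definition of evaluability.

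A reader might infer that the DLT is certain to vanish from both the primary and the safety analyses. The documents do not support that. The protocol keeps the patient in the treated set and the safety analysis, and the SAP is based on protocol section 7 and declares no change. The SAP 6.3 phrase can be read as naming the Part II regimen, in parallel with its wording for monotherapy. SAP 6.1 also starts the on-treatment period at first intake of study drug.

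A reader might also infer that every severe reaction during the first infusion is lost. It is lost only if BI 836880 is never given. Protocol 5.2.9.1.4 says and/or, and protocol 4.1.6 lets the other drug continue when causality to one drug is unequivocal. A patient who does receive BI 836880 satisfies 4.1.8.

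Lastly, a reader might infer that one lost DLT at 120/240 opens 360/240. On 0/2 it does not (0.291). It would need a top-up to 0/3 (printed 0.248, recomputed 0.253, so right at the limit), and protocol 3.3.4.1 bars replacing a patient who comes off trial for a DLT.

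**Conclusion.** The point holds as a contradiction between definitions. On its literal wording, 4.1.8, through protocol 7.3 and the SAP dose escalation set, drops a cycle 1 DLT from the MTD analysis because toxicity prevented the second infusion. Protocol 4.1.7 and 7.3.2 and SAP 7.4 would count it. For safety the defect is smaller: an ambiguous SAP phrase set against clear protocol text.

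The event is probably uncommon, but one case can move 360/240 from failing EWOC (about 0.295) to meeting it (about 0.12). That size rests on the model in 7.1.2 with the prior rows exchanged so as to match the printed tables, and on the patient being dropped without replacement. The prior is to be updated with actual data, so the probabilities at the time of a real decision will differ. The 46-patient figure assumes that the DLT criteria of the monotherapy trials, which the documents do not give, are comparable.

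**What to change.** - **Protocol 4.1.8:** state that a Part II patient with a cycle 1 DLT after any amount of either trial drug is evaluable, and that a DLT-free Part II patient is evaluable only after receiving both drugs and completing cycle 1.
- **SAP 6.3:** define the Part II treated set as any administration, including partial, of BI 836880 or ezabenlimab, to match protocol 7.3.1. Let the Part II dose escalation set refer to the revised 4.1.8.
- **Replacement:** reconcile both definitions with protocol 3.3.4.1, so that a patient with such a DLT cannot be classed as non-evaluable and then replaced.

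The cost is wording in two sections and one cross-reference. It needs no new data or patients and leaves dosing and treatment-stopping rules unchanged. It should be in place before the Part II dose decisions and the final analysis.

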4.1.9 Blinding and procedures for unblinding

4.1.9.1 Blinding

Not applicable, as this is an open-label, single-arm trial.

4.1.9.2 Unblinding and breaking the code

Not applicable

4.1.10 Packaging, labelling, and re-supply

The investigational medicinal products will be provided by BI or a designated Contract Research Organisation (CRO). They will be packaged and labelled in accordance with the principles of Good Manufacturing Practice (GMP). Re-supply to the sites will be managed via an Interactive Response Technology (IRT) system, which will also monitor expiry dates of supplies available at the sites.

For details of packaging and the description of the label, refer to the ISF.

4.1.11 Storage conditions

Drug supplies will be kept in their original packaging and in a secure limited access storage area according to the recommended storage conditions on the medication label. A temperature log must be maintained for documentation.

If the storage conditions are found to be outside the specified range, the Clinical Research Associate (CRA) must be contacted immediately.

4.1.12 Drug accountability

The investigator or designee will receive the investigational drugs delivered by the sponsor when the following requirements are fulfilled:

- Approval of the clinical trial protocol (CTP) by the Institutional Review Board (IRB) / Independent Ethics Committee (IEC),
- Availability of a signed and dated clinical trial contract between the sponsor and the investigational site,

Proprietary confidential information © 2019 Boehringer Ingelheim International GmbH or one or more of its affiliated companies

- Approval/notification of the regulatory authority, e.g. competent authority (CA),
- Availability of the curriculum vitae of the Principal Investigator,
- Availability of a signed and dated CTP

Investigational drugs are not allowed to be used outside the context of this protocol. They must not be forwarded to other investigators or clinics.

The investigator or designee must maintain records of the product's delivery to the trial site, the inventory at the site, the use by each patient, and the return to the sponsor or warehouse / drug distribution centre or alternative disposal of unused products. If applicable, the sponsor or warehouse / drug distribution centre will maintain records of the disposal.

These records will include dates, quantities, batch / serial numbers, expiry ('use- by') dates, and the unique code numbers assigned to the investigational medicinal product and trial patients. The investigator or designee will maintain records that document adequately that the patients were provided the doses specified by the CTP and reconcile all investigational medicinal products received from the sponsor. At the time of return to the sponsor, the investigator or designee must verify that all unused or partially used drug supplies have been returned by the clinical trial patient and that no remaining supplies are in the investigator's possession.

4.2 OTHER TREATMENTS, EMERGENCY PROCEDURES, RESTRICTIONS

4.2.1 Other treatments and emergency procedures

There are no other mandatory treatments to be used or special emergency procedures to be followed.

Potential side effects of BI 836880 or BI 754091 have to be treated symptomatically. Symptomatic treatments of side effects or tumour-associated symptoms are allowed.

4.2.1.1 Permitted concomitant medications

- If medically feasible, patients taking regular medication should be maintained on it throughout the trial.
- Pre-medication is not required, but may be utilised following the first dose of study medication. This includes medications for the management of nausea, diarrhoea, and vomiting for which the patient must be treated according to institutional standards.
- Supportive care and other medications that are considered necessary for the patient's well-being may be given at the discretion of the Investigator.
- Blood transfusions are allowed at any time during the trial, except to meet inclusion criteria.

4.2.2 Restrictions

4.2.2.1 Restrictions regarding concomitant treatment

- No other investigational therapy or anticancer agent should be given to patients. If such agents are required for a patient, then the patient must first be withdrawn from the trial.
- Immunosuppressive medications including, but not limited to systemic corticosteroids at doses exceeding 10 mg/day of prednisone or equivalent, methotrexate, azathioprine, and tumour necrosis factor-alpha blockers are prohibited. Use of immunosuppressive medications for the management of investigational product-related AEs or in patients with contrast allergies is acceptable, and does not necessarily warrant immediate treatment discontinuation. In addition, use of inhaled, topical, intranasal corticosteroids or local steroid injections (e.g., intra-articular injection) is permitted. Temporary uses of corticosteroids for concurrent illnesses (e.g., food allergies, computed tomography [CT] scan contrast hypersensitivity) are acceptable.
- Live attenuated vaccines are prohibited during the trial through 30 days after the last dose of investigational product.
- Patients already receiving erythropoietin at the time of screening for the trial may continue it, provided they have been receiving it for more than one month at the time trial treatment is started. Prophylactic erythropoietin should not be started during the first 3 weeks of any cohort, but may be started thereafter.
In Japan, no erythropoietin product is approved for anaemia associated with cancer chemotherapy.
- Prophylactic granulocyte colony stimulating factors, and palliative radiotherapy are not allowed during the first 3 weeks.
- For symptom control, palliative radiotherapy is permitted for any lesion, except during the first cycle as it could interfere with the DLT evaluation for MTD/RP2D determination. Lesions that have been exposed to radiotherapy are no longer evaluable, and may not be included in the assessment of the non-target lesions and the overall assessment. These lesions may also not be used for a trial biopsy.
- Full-dose anticoagulation (according to local guidelines) with Vitamin K antagonist and other anticoagulation are not allowed during the trial conduct; LMWH is allowed only for prevention but not for curative treatment.
- Any planned surgeries are not allowed (see Exclusion Criteria Section [3.3.3](#) for further details). Unplanned surgeries should be postponed whenever possible four weeks after stop of treatment. For urgent interventions patients should not be further treated and should be intensely monitored regarding wound healing and post-operative complications.

